1.3. Sample Size and Power

No formal power or sample size calculations were applied.

2. TYPE OF PLANNED ANALYSIS

2.1. Interim Analysis

No formal interim analyses will be conducted.

2.2. Final Analysis

Final analysis will be performed after all participants have completed the registry study or have prematurely discontinued from the registry, outstanding data queries have been resolved or adjudicated as unresolvable, and the data have been cleaned and finalized.

3. GENERAL CONSIDERATIONS FOR DATA ANALYSES

Descriptive statistics will be generated for this registry study. For categorical variables, the number and percentage of participants in each category will be presented; for continuous variables, the number of participants (n), mean, standard deviation (SD) or standard error (SE), median, first quartile (Q1), third quartile (Q3), minimum, and maximum will be presented.

By-participant listings will be presented for all participants in the All Enrolled Analysis Set and sorted by participant ID number, visit date, and time (if applicable). Data collected on log forms, such as adverse events (AEs), will be presented in chronological order within the participant. Age, sex at birth, race, and ethnicity will be included in the listings, as space permits.

3.1. Analysis Sets

3.1.1. All Enrolled Analysis Set

All Enrolled Analysis Set includes participants who signed the informed consent and enrolled into the study.

3.1.2. Full Analysis Set

The Full Analysis Set (FAS) includes all participants who met all inclusion criteria and did not meet any of the exclusion criteria, and with at least one post-enrollment visit measurement available. We have 34 participants in total enrolled but not included in FAS (32 participants recorded with criteria not met in eCRF and 2 more participants who received PEG/INF in the parent study but without exclusion records in eCRF). This is the primary analysis set for endpoint analyses.

3.1.3. Safety Analysis Set

The definition of the safety analysis set will be the same as the definition of the FAS.

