##### **8.2.1. Analysis Sets**

###### **8.2.1.1. Safety Analysis Set**

The analysis set includes all enrolled subjects. Both the safety and efficacy analyses will be based on the safety analysis set.

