## **8.7. Safety Analysis**

Analysis of safety measures will be descriptive and will include subjects in the Safety analysis set. Missing observations will be excluded from analysis of safety measures. All safety data collected on or after the date of enrollment through the remainder of the study will be summarized.

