### **8.7.2. Adverse Events**

Clinical and laboratory adverse events will be coded using the Medical Dictionary for Regulatory Activities (MedDRA). System Organ Class (SOC), High-Level Group Term (HLGT), High-Level Term (HLT), Preferred Term (PT), and Lower-Level Term (LLT) will be attached to the clinical database.

Events will be summarized by the date of onset for the event. An adverse event is defined as an event that begins or worsens on or after the date the ICF is signed through study completion or study discontinuation and is classified as related to study procedure.

Adverse events, including SAEs by the above definition, will be listed by subject. The frequency of subjects who experience adverse events will be summarized overall, by treatment regimen and by severity.

SAEs that do not meet the above definition will not be captured or summarized.

Data listings will be provided for subjects who discontinued the study due to an adverse event by the above definition.

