7.1.4. Summaries of Adverse Events and Deaths

A brief high-level summary of study procedure related AEs will be provided by treatment group and overall, including the number and percentage of participants who experienced at least 1 AE in the following categories: any AE, any AE of Grade 2 or above, any AE of Grade 3 or above, any SAE, and AE leading to premature discontinuation of study. All deaths (including those that are procedure related and those that are not procedure related) observed during the study will also be summarized and included in this table.

AE summaries will provide the number and percentage of participants for reported AEs by treatment group and by SOC and PT based on the Safety Analysis Set as follows:

- All AEs
- All AEs with Grade 3 or above
- All AEs by grade
- All SAEs
- AEs leading to premature discontinuation of this registry study

Multiple events will be counted only once per participant in each summary. Adverse events will be summarized and listed first in alphabetic order of SOC (and HLT within each SOC if applicable), and then by PT in descending order of total frequency within each SOC. For summaries by severity grade, the most severe grade will be used for those AEs that occurred more than once in an individual participant during the study.

In addition to the above summary tables, all AEs, all AEs by grade will be summarized by treatment group and by PT only, in descending order of total frequency.

By-participant listings will be provided by participant ID number in ascending order for the following:

- All AEs
- AEs of Grade 3 or above
- SAEs
- All deaths (with a flag indicating liver-related death identified by Clinical Research)
- All AEs leading to premature discontinuation of this registry study

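### SAP 3.1.3 narrows the Safety Analysis Set from all enrolled to the FAS, so 34 enrolled participants fall outside the AE summaries while SAP 7.3 reports no change from the protocol

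*SAP*

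**What the plan says.** **Protocol.** Section 8.2.1.1 defines a single set: "The analysis set includes all enrolled subjects. Both the safety and efficacy analyses will be based on the safety analysis set". Section 8.7 uses that set for safety and adds: "All safety data collected on or after the date of enrollment through the remainder of the study will be summarized". Section 8.7.2 says how: "The frequency of subjects who experience adverse events will be summarized overall, by treatment regimen and by severity". Its AE window opens when consent is signed.

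**SAP analysis sets.** Section 3.1.1 keeps a set of the protocol's kind: "All Enrolled Analysis Set includes participants who signed the informed consent and enrolled into the study". Section 3.1.2 then defines the FAS by two conditions: all eligibility criteria satisfied, and at least one measurement after enrollment. It gives the count outside the FAS: "We have 34 participants in total enrolled but not included in FAS (32 participants recorded with criteria not met in eCRF", together with "2 more participants who received PEG/INF in the parent study but without exclusion records in eCRF". Section 3.1.3 closes the loop: "The definition of the safety analysis set will be the same as the definition of the FAS".

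**SAP use of the sets.** The opening of Section 7 puts safety measures on the Safety Analysis Set, and 7.1.4 repeats this for the tables of "reported AEs by treatment group and by SOC and PT based on the Safety Analysis Set as follows". Section 6 puts primary and secondary endpoints on the FAS. Section 3.2 removes participants on interferon-based regimens from the FAS and from every analysis. Sections 6.5 (endpoints) and 7.3 (safety) each state that no change from the protocol is planned.

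**The concern.** The protocol specified the population for the AE summaries. The SAP replaced it with a smaller one, and the sections meant for declaring such departures say there is none. A reader who relies on 7.3 would take the AE percentages to describe everyone enrolled.

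Eligibility is a weak reason for leaving people out of these particular tables. The registry gives no treatment and records only AEs related to its own procedures. The schedule of blood draws and endoscopy is the same for every enrolled participant, eligible or not. The second FAS condition also fits poorly with a safety set: someone harmed by a Day 1 procedure who never came back would fail it. The documents report no such case, and none is claimed here.

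**Working it through.** **1. The SAP's own count.** From SAP 3.1.2: 32 with criteria not met in the eCRF, plus 2 who received pegylated interferon without an exclusion record. 32 + 2 = 34, as stated. This breakdown attributes all 34 to eligibility or interferon. It shows no separate number for participants without a post-enrollment measurement, so either there were none or they are not counted. The 2 are also not the total treated with interferon, since others may be among the 32.

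**2. Population under each document.**

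| Item | Protocol | SAP |
|---|---|---|
| Safety set | all enrolled (8.2.1.1) | FAS (3.1.3) |
| AE summaries | all enrolled (8.7, 8.7.2) | FAS (7, 7.1.4) |
| Endpoint analyses | all enrolled (8.2.1.1) | FAS (6) |
| By-participant listings | individual data listed (8.2) | all enrolled (3) |
| Declared change, safety | – | none (7.3) |
| Declared change, endpoints | – | none (6.5) |

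The AE-summary and endpoint rows differ between the documents, so 7.3 and 6.5 are each inaccurate on the analysis set.

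**3. Tables affected.** SAP 7.1.4 plans 1 high-level overview, 5 tables by SOC and PT (all AEs, Grade 3 or above, by grade, SAEs, AEs leading to discontinuation) and 2 by PT only (all AEs, by grade). 1 + 5 + 2 = 8. The overview also carries deaths. There 7.1.4 speaks of all deaths observed during the study, while the opening of Section 7 limits safety measures to the Safety Analysis Set. Two programmers could produce different death rows.

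**4. Effect on a percentage.** Let N be the number enrolled, E the participants with an event among all N, and e those among the 34. If the 34 are everyone outside the FAS, the protocol's percentage is E/N and the SAP's is (E − e)/(N − 34). The SAP figure is higher when e/34 < E/N and lower when e/34 > E/N. The documents give none of N, E or e, so neither the direction nor the size can be settled.

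For scale only, with N assumed, and with the ratio computed for the case e = 0:

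| Assumed N | 34/N | N/(N − 34) |
|---|---|---|
| 500 | 6.8% | 500/466 = 1.073 |
| 1,000 | 3.4% | 1000/966 = 1.035 |
| 2,000 | 1.7% | 2000/1966 = 1.017 |

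The middle column is a share of participants, not a shift in any AE rate.

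**The case against.** The strongest reply is that the SAP is open about the restriction. Section 3.1.2 gives both conditions, the count and the reasons; 3.2 states the interferon exclusion; 4.1 tabulates enrolled, FAS and Safety Analysis Set numbers; and 4.3 lists ineligible enrollees. The study is descriptive, with no hypothesis test, and AE, SAE and death listings are planned for all enrolled. Most of this stands. A reader might infer that the exclusion is concealed, but the documents do not support that. What is missing is any statement that the set departs from the protocol, and 7.3 and 6.5 say the opposite. Protocol 8.10 leaves additional analyses and methods to the SAP; it does not cover replacing a defined set while reporting no change.

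A second reply is that the registry's target population is interferon-free. That can justify the FAS for endpoints. It does not explain removing the same people from summaries of procedure-related harm.

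A third reply is that the documents do not say which procedures the 34 underwent or how long they stayed. If some had none, an all-enrolled denominator would dilute the percentages. That is fair, and it is a reason to claim no bias in either direction. It does not alter what the protocol specified.

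Two further inferences go too far. One is that AEs or deaths among the 34 are lost from the report: the planned listings cover everyone enrolled. The other is that certainly nothing is lost: 3.2 removes interferon-treated participants from every analysis, and how this fits with all-enrolled listings is not resolved.

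**Conclusion.** The discrepancy is real and follows directly from the text. The SAP's Safety Analysis Set is narrower than the protocol's; 34 enrolled participants are outside the 8 AE summaries, in numerator and denominator; the population for the death row is ambiguous; and 7.3 is wrong to report no change. SAP 6.5 is wrong in the same way, because Section 6 uses the FAS where the protocol uses all enrolled.

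A reader might go on to conclude that the AE rates are materially distorted. The documents do not support that: total enrolment and the events among the 34 are not given. The effect is probably small, and the shares above rest on assumed enrolment. This should be corrected because the departure is undeclared and the remedy is cheap, not because a wrong rate has been shown.

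**What to change.** **Preferred.**
1. In SAP 3.1.3, define the Safety Analysis Set as all enrolled participants (the 3.1.1 set) and use it for every Section 7 summary. State in 7.1.4 that this includes the death row.
2. In 3.2, limit the interferon exclusion to endpoint analyses. In the Section 7 tables, show interferon-treated participants as their own regimen group, SOF+RBV+PEG, which Appendix 12.3 already defines. The groups then sum to Total and the by-regimen summary in protocol 8.7.2 is kept.
3. Name the FAS in 5.1 and 5.2, which now refer to the safety set, so that the baseline tables still match the endpoint tables.
4. In 6.5, declare that endpoint analyses use the FAS instead of the protocol's all-enrolled set, naming both its eligibility and its post-enrollment-measurement conditions.

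**Minimum.** If the Safety Analysis Set is not restored, make the 6.5 declaration, declare and justify the safety-set change in 7.3, and report AEs and deaths among the excluded participants separately.

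**Cost.** No new data and no new population. The preferred route needs wording edits in 3.1.3, 3.2, 5.1, 5.2, 6.5 and 7.1.4 of a signed SAP, one added regimen column and a rerun of the Section 7 tables. SAP Section 1 provides for documenting later changes in the CSR. The downside is that AE and endpoint tables would have different denominators, which a footnote can explain. The minimum route costs one statement each in 6.5 and 7.3 plus a short separate report on the excluded participants.

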3.2. Participant Groups

All analyses will be performed and summarized by treatment groups.

Treatment groups are the treatment regimens that led to SVR during the respective parent studies or the treatment regimens received by commercial participants.

For all analyses, treatment regimens will be classified as SOF+RBV, LDV/SOF±RBV, SOF/velpatasvir (VEL)±RBV, SOF/VEL/voxilaprevir (VOX)±RBV, Other, and Total. Details are shown in Appendix 12.3. Participants completing interferon-based regimens such as those with prior treatment being SOF+PEG+RBV will be excluded from the Full Analysis Set and all analyses.

In addition, analyses of events associated with clinical progression of liver diseases and HCC will be performed and summarized by Child-Turcotte-Pugh (CTP) class calculated upon entry into the registry. CTP score will be classified as A (5-6), B (7-9), or C (10-15) in [Table 6-1](#) and [Section 6.1.3.2.3](#).

3.3. Strata and Covariates

There are no randomization strata or covariates in this observational study.

3.4. Examination of Participant Subsets

No further subset of participants will be examined.

3.5. Multiple Comparisons

No formal statistical hypothesis testing will be conducted. Multiple comparisons are not applicable.

3.6. Missing Data and Outliers

3.6.1. Missing Data

A missing data point for a given registry visit window may be due to any of the following reasons:

- A visit occurred in the window but data were not collected or were unusable
- A visit did not occur in the window
- A participant permanently discontinued from the study before reaching the window

In general, missing data will not be imputed unless methods for handling missing data are specified. Exceptions are presented in this document.

3.6.2. Outliers

Outliers will be identified during the data management and data analysis process, but no sensitivity analyses will be conducted. All data will be included in the data analysis.

3.7. Data Handling Conventions and Transformations

Age (in years) on the registry start date (i.e., Day 1 Visit of the registry collected from the demographic eCRF) and sex at birth will be used for analyses and presentation in listings. If age at Day 1 is not available for a participant, then age derived based on date of birth and the Day 1 visit date will be used instead. For screen failures, the date when the first informed consent was signed will be used for the age derivation.

The following conventions will be used for the imputation of date of birth when it is partially missing or not collected:

- If only month and year of birth is collected, then “15” will be imputed as the day of birth
- If only year of birth is collected, then “01 July” will be imputed as the day and month of birth
- If year of birth is missing, then date of birth will not be imputed.

For some countries, only birth year is collected on the eCRF. In those cases, “01 July” will be used for the unknown birth date and month for the purpose of age calculation, unless age is captured on the eCRF.

When calculating duration of follow-up, time to events such as HCC occurrence and death, partial dates will be imputed as 01 if only day is missing, as 01 January if day and month are missing; and if the imputed death date was before the last available visit date for a participant, the partial death date will be re-imputed as the same of the last available visit date.

For an HCC event that is reported in multiple visits, the earliest diagnosis date is used as the first HCC event occurrence date.

For an endoscopy/liver imaging test conducted on one day but repeatedly reported in multiple visits, it will be assigned to the correct analysis window as in Section 3.8.2. The milder record will be selected for baseline if there are different reported test results (e.g., varices present = “No” will be chosen over varices present = “Yes”, varices grade = “Unknown” will be chosen over varices grade = “Small”), and the more severe record will be selected for postbaseline visits.

Data that are continuous in nature but are less than the lower limit of quantitation (LOQ) or above the upper LOQ will be imputed as follows:

- A value that is one unit less than the lower LOQ will be used for calculation of descriptive statistics if the datum is reported in the form of “< x” (where x is considered the lower LOQ). For example, if the values are reported as < 50 and < 5.0, values of 49 and 4.9, respectively, will be used for calculation of summary statistics. An exception for this rule is any value reported < 1 or < 0.1, etc. For the values reported as < 1 or < 0.1, value of 0.9 or 0.09 will be used for calculation of summary statistics.
- A value that is one unit above the upper LOQ will be used for calculation of descriptive statistics if the datum is reported in the form of “> x” (where x is considered the upper LOQ). Values with decimal points will follow the same logic as above.
- The lower or upper LOQ will be used to calculate descriptive statistics if the datum is reported in the form of “≤ x” or “≥ x” (where x is considered the lower or upper LOQ, respectively).

The Roche Taqman HCV test (lower limit of quantification [LLOQ] = 25 international unit [IU]/mL) was used to measure HCV RNA until 04 JAN 2015 after which the COBAS® AmpliPrep/COBAS® TaqMan® HCV Quantitative Test v2.0 (LLOQ = 15 IU/mL) was used.

For numerical HCV RNA data, values below LLOQ will be set to the LLOQ – 1 IU/mL (i.e., 24 or 14 HCV RNA IU/mL, depending the date of measurement). HCV RNA values reported as “target not detected” will also be set to LLOQ – 1 IU/mL. The original values will be provided in the HCV RNA listings.

For selected analyses, HCV RNA data in IU/mL will be transformed to the logarithmic base 10 scale (i.e., \log_{10} IU/mL).

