3.8.3. Selection of Data in the Event of Multiple Records in a Window

Depending on the statistical analysis method, a single value may be required for each analysis window. For example, change from baseline by visit usually requires a single value, whereas a time-to-event analysis would not require one value per analysis window.

If multiple valid non-missing measurements exist in an analysis window, records will be chosen based on the following rules if a single value is needed, unless otherwise specified.

For baseline:

- The record closest to the nominal day for baseline will be selected except for HCV RNA, for which the latest record in the analysis window will be selected.
- If there are 2 records that are equidistant from the nominal day, the later record will be selected.
- If there are multiple records with the same time or no time recorded on the same day, the baseline value will be the average of the measurements for continuous data, or the measurement with the lowest severity (e.g., normal will be selected over abnormal) for categorical data.

For postbaseline values:

- The record closest to the nominal day for that visit will be selected except for HCV RNA, for which the latest record in the analysis window will be selected.
- If there are 2 records that are equidistant from the nominal day, the later record will be selected.
- If there is more than 1 record on the selected day, the average will be taken for continuous data and the worse severity (e.g., abnormal will be selected over normal) will be taken for categorical data, unless otherwise specified.

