6.4.2. Liver Imaging, Biopsy, Endoscopy and Transplant

Imaging of the liver will be performed as part of standard of care (e.g., CT, MRI, or Ultrasound results, if available). Liver biopsy will be performed at any time only if results available from biopsy performed as part of standard of care. An endoscopy will be performed to evaluate for varices at any time or at Day 1 (+/- 6 months) and within 6 months prior to Week 240 visit as in protocol. Liver transplant will be reported during the study.

A shift table of varices grade from endoscopy (no varices/small varices/large varices/unknown) from Day 1 to Week 240 will be provided by treatment group and baseline CTP class (CTP A, B, C, Unknown and total).

The results of all above will be listed by participant ID number and study visit. Results of endoscopy/imaging/biopsy collected at Day 1 visit but with a procedure date before or on the most recent HCV treatment end date will be flagged in the listing.

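### Conflicting endoscopy or imaging reports are resolved to the milder result at baseline and the more severe result afterwards, so residual conflicts can create apparent worsening but not apparent improvement

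*SAP*

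**What the plan says.** SAP 3.7 addresses a narrow case: "For an endoscopy/liver imaging test conducted on one day but repeatedly reported in multiple visits". The test is first placed in its analysis window. If the reported results differ, severity decides, in opposite directions at the two times: "The milder record will be selected for baseline if there are different reported test results", "and the more severe record will be selected for postbaseline visits". One of its examples for baseline reads "varices grade = “Unknown” will be chosen over varices grade = “Small".

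SAP 3.8.3 has a parallel rule when several categorical records fall on the same day. At baseline it takes "the measurement with the lowest severity (e.g., normal will be selected over abnormal) for categorical data"; after baseline "the worse severity (e.g., abnormal will be selected over normal) will be taken for categorical data". Its scope is limited in three ways:

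- Same-day continuous values are averaged at both times.
- Records from different days are chosen by closeness to the nominal day (for HCV RNA, the latest in the window), in the same way before and after baseline.
- The baseline clause covers records with the same time or no time; the post-baseline clause covers any records on the selected day.

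Two planned outputs use endoscopy or imaging results in an analysis. SAP 6.4.2 plans "A shift table of varices grade from endoscopy (no varices/small varices/large varices/unknown) from Day 1 to Week 240", by treatment group and baseline CTP class. SAP 6.1.3.2.1 takes ascites from liver imaging and counts it as both a progression event and a decompensation event. Protocol 8.6.2 names varices and ascites among the signs of progression or regression. Neither document gives a reason for the asymmetry or plans an analysis with one rule at both times.

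**The concern.** Two reports of the same test on the same day cannot both be right, and nothing in the documents suggests that the error leans one way before Day 1 and the other way after it. Resolving conflicts downward at baseline and upward afterwards turns reporting inconsistency into apparent progression.

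Taking the worst post-baseline value is a familiar cautious convention in drug-safety summaries. Here no drug is given, and the second primary endpoint (protocol 8.1.2, SAP 6.1.1) is two-directional. The registry has no untreated comparator, so the reported proportions are themselves the result and the bias has no control arm to cancel against. At stake is whether a shift table read as change over five years partly reflects how duplicate entries were resolved.

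**Working it through.** The plan gives no figure to reproduce: no sample size calculation and no conflict frequency. The check is whether the direction follows from the rule, how large the effect is under stated assumptions, and which outputs it reaches.

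**Inputs.** From SAP 3.7 and 3.8.3: minimum severity at baseline, maximum after baseline. Assumed: a share d of tests with conflicting reports at each time (1% to 10%), and prevalence v of the finding (20% or 40%). In each conflict, one of the two reports is taken to be correct.

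**1. Direction.** Let B be the set of reported grades at baseline and P the set after baseline, with true grades b in B and p in P. The apparent change is max(P) − min(B). Since max(P) ≥ p and min(B) ≤ b, it is never less than the true change p − b. The rule can only move a result towards worsening.

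**2. Three grades (none, small, large).** I enumerated every pattern of two reports at each time with at least one conflict, taking each report in turn as the true one. This gives (3×1 + 6×2)² − 9 = 216 cases. These are counts of patterns, not probabilities, and unknown grades are left out.

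| True change | Cases | Shown as improved | Shown as unchanged | Shown as worse |
|---|---|---|---|---|
| Improvement | 72 | 8 | 24 | 40 |
| None | 72 | 0 | 16 | 56 |
| Worsening | 72 | 0 | 0 | 72 |

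**3. Two levels (absent, present), no true change.** If the finding is truly absent, baseline always reads absent and the later value reads present with probability d. If truly present, baseline reads absent with probability d and the later value always reads present.

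- False worsening = (1 − v)·d + v·d = d, whatever v.
- False improvement = 0.

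For d = 1%, 2%, 5% and 10%, false worsening is 1%, 2%, 5% and 10%, against 0% false improvement each time.

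**4. One rule at both times, d = 5%.**

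- Milder at both: v·d·(1 − d) each way. At v = 20%, 0.20 × 0.05 × 0.95 = 0.95% worse and 0.95% better; at v = 40%, 1.90% and 1.90%.
- More severe at both: (1 − v)·d·(1 − d) each way. At v = 20%, 3.80% and 3.80%; at v = 40%, 2.85% and 2.85%.
- A rule blind to severity that picks the correct report half the time: (d/2)·(1 − d/2) = 0.025 × 0.975 = 2.44% each way, whatever v.

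The balance in step 4 needs equal conflict rates at the two times. With rates d₁ and d₂, more severe at both leaves a net (1 − v)(d₂ − d₁), and the blind rule leaves (1 − 2v)(d₂ − d₁)/2. For example, with d₁ = 5%, d₂ = 2% and v = 20%, these are 0.8 × (−3) = −2.4 and 0.6 × (−3)/2 = −0.9 percentage points. A Day 1 test has more later visits at which it can be reported again, so unequal rates are plausible.

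**5. Reach.** The varices table compares exactly the two times that are handled oppositely. For ascites, a post-baseline imaging conflict would resolve towards an event. This route is possible, not certain: the analysis is time to first event, SAP 3.8.3 notes that such analyses need no single value per window, and minimal or trace ascites is not counted. The SAP also does not say whether the milder-baseline rule decides who is excluded for a prior event.

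**6. Unknown grades.** If the baseline reports are unknown and small, the participant enters the table as unknown. A true small-to-large and a true small-to-none change are then equally invisible.

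**The case against.** The strongest defence is that the effect is rare and contained. Protocol 9.1.6 has data discrepancies queried at sites, and SAP 2.2 places the final analysis after queries are resolved or judged unresolvable, so only residual conflicts matter. The rule is prespecified, the analyses are descriptive with no tests, and SAP 6.4.2 lists endoscopy and imaging results by participant and visit, so affected cases should be traceable. The direction also works against showing regression after SVR, which can be called conservative. A differing later entry may be a correction rather than noise. All of this limits the size and stands. It does not justify opposite rules at the two times for a two-directional question.

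Several stronger readings are tempting, and the documents do not support them:

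- *Imaging shift tables are biased.* None is planned. SAP 6.4.2 has a shift table only for varices, under 'Other Measurements'; imaging results are listed.
- *The primary endpoint as a whole is tilted and regression is hidden.* Continuous measures such as MELD, FIB-4 and elastography values are averaged when same-day records repeat, and different-day records are selected symmetrically. The varices event in the primary list is bleeding, taken from the liver disease assessment page, not endoscopic grade.
- *Improvement can never appear.* The rule creates none, but a true improvement can survive on the graded scale, as 8 of the 72 enumerated cases show.
- *The unknown-grade rule adds to the bias towards worsening.* It loses information in both directions and is a separate defect.

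**Conclusion.** The point holds within its scope. For endoscopy and imaging tests with unresolved conflicting reports, and for same-day categorical records, the rule can produce apparent worsening, cannot produce apparent improvement, and understates true improvement. That direction follows from the rule, given only that the true grade is among those reported.

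The size is not known. In the two-level model false worsening equals the conflict rate, so 1% to 10% is simply the assumed range carried through; the actual rate may be lower. The varices shift table is affected directly. The progression and decompensation Kaplan-Meier analyses are affected only if the rule is applied to imaging-based ascites, which the SAP leaves open. A reader might infer that the registry's reported progression is materially overstated; without a conflict rate the documents cannot support that. The case for change is that a built-in directional bias can be removed at almost no cost.

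**What to change.** - In SAP 3.7, and for categorical data in 3.8.3, use one rule at baseline and after baseline that ignores severity, for example the record entered closest to the procedure date. Where the source report can be checked, let it settle the conflict, since a later entry may be a correction.
- Treat an unknown grade as missing whenever a known grade exists for the same test.
- State whether the 3.7 rule governs imaging-based ascites, both for counting events and for excluding participants with prior events.
- Report the number of conflicting tests by time point.
- If the present rule is kept, add a version of the varices shift table and the ascites events under one rule at both times.

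Using the more severe record at both times is a weaker choice: it overstates prevalence at both times and balances only if conflict rates are equal.

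The cost is a few sentences and one count, with no new data collection. SAP section 1 already provides for later changes to be documented in the CSR. The downside is a departure from the sponsor's convention, and it affects only participants with conflicting duplicates.
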